10.6 Assessing "expectedness"

The assessment of expectedness will be performed by the Chief Investigator (or agreed delegate), not by the site research team.

All safety events assessed as "serious" and "related" will be assessed as expected and classified as RUSAEs if they meet the following criteria:

- Repeat fall during therapy sessions
- Repeat fracture during therapy sessions
- Other accident of injury during therapy sessions

10.7 Follow-up after Adverse Events

All safety events should be followed until satisfactory resolution or until the investigator responsible for the care of the participant deems the event to be chronic or the patient to be stable. When reporting serious events (SAEs / related SAEs / RUSAEs) the investigator responsible for the care of the participant should apply the following criteria to provide information relating to event outcomes: resolved; resolved with sequelae (specifying with additional narrative);; ongoing at final follow-up; fatal or unknown.

10.8 Reporting Procedures

All safety events will be recorded and reported for each patient participant from the period of randomisation until their final 52 week follow-up assessment.

Depending on the nature of the event the reporting procedures below should be followed. Any questions concerning safety event reporting should be directed to the CTRC in the first instance.

10.8.1 Non serious safety events (AEs / related AEs)

All such events, whether related or not, should be recorded on an Adverse Event Form and entered into the trial database (see section 10.2 for reportable events).

10.8.2 Serious safety events (SAEs / related SAEs / RUSAEs)

All serious events related to intervention, and whether expected or not should be recorded on an SAE form. The SAE form asks for the nature of event, date of onset, severity, corrective therapies given, outcome and causality. The responsible investigator should sign the causality of the event.

SAEs **related** to the intervention (related SAEs / RUSAEs) should be reported to the CTRC within 24 hours of the local site becoming aware of the event. SAEs that are **not related** to the intervention (SAEs) should be entered into the trial database at 17 or 52 weeks.

Local Principal Investigators should report any SAEs as required locally.

All serious events (SAEs / related SAEs / RUSAEs) will be reported annually to the REC and periodically to the IDSMC by the CTRC. Unexpected, related and serious events (RUSAEs) will also be reported in an expedited manner (15 days from CTRC being aware) to REC.

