3 INTRODUCTION

3.1 Background

Proximal femoral fracture, more commonly referred to as hip fracture, is a common, major health problem in old age. The total number of patients entered onto the national hip fracture database in England, Wales and Northern Ireland in 2015 was 65,645¹. As the population ages the number of elderly people falling and fracturing their hips is projected to increase further^{2,3}. Such fractures are strongly associated with decreased bone mineral density, increased age, prior fragility fracture, cognitive impairment, under-nutrition, frailty, poor physical functioning, vision problems, weight loss and other health problems⁴. Mortality is high with 14-58% dying within the following 12 months^{5,6}. A review of the long-term disability associated with proximal femoral fracture found that 29% did not regain their level of functioning after one year in terms of restrictions of activities of daily living⁷. Many who were living independently before their fracture lost their independence afterwards. This imposes a large cost burden on society amounting to about £2.3 billion a year in the United Kingdom equating to approximately £6 million a dav⁸. Tian et al.⁹ explored Torbay's (Devon) unique patient-level linked data set of National Health Service (NHS) and social care costs for older people in the 12 months before and after being admitted to hospital as a result of a fall. They found that the cost of hospital, community and social care cost services for each patient were almost four times as costly in the 12 months after admission, compared with the costs of the admission itself, and that the majority of costs occurred outside of the acute hospital setting. Particularly frail individuals may go onto have a further proximal femoral fracture resulting in additional disability and deaths¹⁰.

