9 PARTICIPANT TIME LINE, ASSESSMENTS AND PROCEDURES

9.1 Schedule for Follow-up

Participant follow-up visits should take place at 17 and 52 weeks post randomisation

Procedures	Screening	Baseline / Randomisation *	Trial intervention**	17 weeks post randomisation Follow-up	Qualitative interviews	52weeks post randomisation Follow-up
Eligibility screening and consent						
Assessment of eligibility criteria	Х					
Written and informed consent (patient / carer))	х					
Confirm consent		Х	Х	Х	Х	Х
Randomisation		Х				
Discharge data		Х				
Outcome measurement - patient						
NEADL		х		Х		Х
HADS		Х		Х		Х
AMTS		Х		Х		Х
VAS hip pain intensity		Х		х		Х
FES-I		Х		Х		Х
VASFoF		Х		Х		Х
EQ-5D-3L		Х		Х		Х
CSRI		Х		Х		Х
Grip strength		Х		Х		Х
SPPB				Х		Х
Outcome measurement - carer						
CSI		Х		Х		Х
HADS		Х		Х		Х
Trial Intervention**			Х			
Qualitative interviews						
Re-affirm consent verbally specifically for qualitative phone interview. (patient / carer)					х	
Qualitative telephone interview					Х	
Safety Event Reporting						
Monitoring of Adverse Events			Х	Х	Х	Х
Monitoring of Serious Adverse Events			Х	Х	Х	Х

* Randomisation and baseline should take place no later than 4 weeks after hip fracture repair surgery

** If randomised to intervention arm.

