10 SAFETY REPORTING

All safety events will be recorded by researchers when they are made aware of the event by the patient, carer, the treating clinicians, or therapists, in accordance with the principles of GCP. Safety event reporting information will be included in the training given to the therapy teams delivering the intervention and they will be given copies of the safety event reporting forms and details of how to enter them on to the trial database or send to the CTRC.

AE reports and SAEs not related to the intervention will be entered on to the remote data entry system at follow-up visits. SAE reports related to the intervention will be completed and sent to the CTRC within 24 hours of becoming aware of the event.

Safety events will be captured on two separate forms: Adverse Events form for all non-serious events and SAEs not related to intervention and a Serious Adverse Events (SAE) form for serious events related to intervention. The SAE form will have two sections, the first is for the healthcare professional to complete at site who will complete information including the seriousness of the event and whether it is related to the trial and return to the CTRC trial manager. The trial manager will liaise with the Chief Investigator (or agreed delegate) who will complete the second part of the form, including an assessment of expectedness for related events.

All SAEs, along with the PI's assessment of whether it is related to the intervention and for related events the CI's assessment of whether or not it is expected, will be reported to the REC annually. All SAEs which are assessed as related and unexpected will be reported to the REC and Sponsor in an expedited manner.

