10.3 Assessing "seriousness"

All safety events will be assessed for "seriousness". The assessment of "seriousness" should be made by the investigator responsible for the care of the participant using the following criteria. Events meeting the below criteria will be classified as "serious" (i.e. SAEs, related SAEs / RUSAEs). A safety event will be assessed as "serious" if it:

- Results in death;
- Is life-threatening (refers to an event during which the participant was at risk of death at the time of the event; it does not refer to an event which might have caused death had it been more severe in nature);
- Is a fall that results in injury and repeat fractures;
- Requires hospitalisation or prolongation of existing hospitalisation;
- Results in persistent/significant disability or incapacity;

• Other important medical events that, based upon appropriate medical judgement, may jeopardise the participant and may require medical or surgical intervention.

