10.9 Responsibilities – Site Principal Investigator

The site Principal Investigator is responsible for recording and reporting to CTRC all safety events that are observed or reported during the trial, regardless of their relationship to the trial. All serious events related to intervention (SAEs / related SAEs / RUSAEs) must be reported immediately by the investigator to the CTU on an SAE form. All other adverse events and serious adverse events not related to intervention should be reported on the regular progress/follow-up reports.

Minimum information required for reporting

- Trial randomisation number
- Sponsor trial number
- One identifiable coded subject
- One identifiable reporter
- A causality assessment
- I. The SAE form should be completed by a designated investigator, a physician named on the 'signature list and delegation of responsibilities log' as responsible for reporting serious safety events and making trial related medical decisions. The investigator should assess the event for the likelihood that it is a response to the trial intervention. In the absence of the designated investigator the form should be completed and signed by an alternative member of the research site trial team (as named on the delegation log) and submitted to the CTRC. As soon as possible thereafter the responsible investigator should check the SAE form, make amendments as appropriate, sign and re-send to the CTRC. The initial report shall be followed by detailed reports every 5 days until resolution.
- II. When submitting a SAE to the CTRC research sites should also telephone the appropriate trial co-ordinator on telephone number [name] to advise that an SAE form has been submitted.
- III. Send the SAE form by fax (within 24 hours or next working day) to the CTU:

[contact]

- I. The responsible investigator must **notify** their R&D department of the event (as per standard local governance procedures).
- II. The participant must be followed-up until clinical recovery is complete and laboratory results have returned to normal, or until the event has stabilised. Follow-up may continue after completion of protocol treatment if necessary.
- **III.** Follow-up information is noted on another SAE form by ticking the box marked 'follow-up' and returning to the CTRC as information becomes available. Extra, annotated information and/or copies of test results may be provided separately.

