11.2.1 Feasibility (attaining recruitment targets)

The phase II trial has provided estimates of the recruitment and retention rates. In a nine-month period between June 2014 and March 2015, 593 patients with proximal femoral fracture were screened for eligibility, of which 266 (45%) were eligible. The main reason for ineligibility was lack of mental capacity (49%). Out of those eligible 193 (73%) were invited to participate and 62 (32% of the eligible population who were invited) agreed to participate. So to recruit 446 we would need to invite 1,394 who are eligible to participate and screen 3,097 patients with proximal femoral fracture. In order to do this we will aim to recruit 12 sites in six geographical locations: Merseyside, North Wales, South Wales, Nottingham, London and East Anglia and recruit participants over 14 months.

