15.3.3 Independent Data and Safety Monitoring Committee (IDSMC)

The independent Data and Safety Monitoring Committee (IDSMC) consists of an independent chairperson, plus 2 independent members who are experts in the field of hip fractures and rehabilitation.

The IDSMC will be responsible for reviewing and assessing recruitment, interim monitoring of safety and effectiveness, trial conduct and external data. The IDSMC will first convene prior to the start of recruitment and will then define frequency of subsequent meetings (at least annually). Details of the interim analysis and monitoring are provided in section 11 and 13.

The IDSMC will provide a recommendation to the TSC concerning the continuation of the trial. Refer to the IDSMC charter and trial oversight committee membership document for further details.

Name	Affiliations	Contribution to protocol
[name]	Department of Health Services Research, University of Liverpool	Chief Investigator
[name]	Clinical Trials Research Centre University of Liverpool Institute of Child Health Alder Hey Children's NHS Foundation Trust Liverpool	Head of Trial Management
[name]	Clinical Trials Research Centre University of Liverpool Institute of Child Health Alder Hey Children's NHS Foundation Trust Liverpool	Supervising Trial Manager
[name]	Clinical Trials Research Centre University of Liverpool Institute of Child Health Alder Hey Children's NHS Foundation Trust Liverpool	Senior Statistician
[name]	Clinical Trials Research Centre University of Liverpool Institute of Child Health Alder Hey Children's NHS Foundation Trust Liverpool	Senior Data Manager
[name]	Clinical Trials Research Centre University of Liverpool Institute of Child Health Alder Hey Children's NHS Foundation Trust Liverpool	Trial Co-ordinator
[name]	Site for Health Economics and	Health Economist

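### Deaths judged unrelated to the intervention may wait until week 17 or 52 for database entry, so those after week 17 need not reach the IDSMC for much of recruitment

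*Protocol*

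**What the plan says.** Three places in the protocol set the timing for SAEs judged unrelated to the intervention.

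- Section 10: "AE reports and SAEs not related to the intervention will be entered on to the remote data entry system at follow-up visits".
- Section 10.8.2: they "should be entered into the trial database at 17 or 52 weeks".
- Section 10.9: "serious adverse events not related to intervention should be reported on the regular progress/follow-up reports".

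Only SAEs judged related go to the trials unit within 24 hours (sections 10 and 10.8.2). Section 10.3 lists "Results in death" as a criterion for seriousness, so a death judged unrelated takes the deferred route. The visits that fix the timing are in section 9.1: "Participant follow-up visits should take place at 17 and 52 weeks post randomisation".

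Sections 9.2.1 and 10 also say that researchers record events when they become aware of them. Neither gives an earlier date by which an unrelated SAE must be in the trial database. The protocol describes no separate death form or death notification.

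Section 15.3.3 gives the IDSMC "interim monitoring of safety and effectiveness, trial conduct and external data", with meetings at least annually. The number of SAEs in each arm is a listed safety endpoint (section 3.4.2).

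**The concern.** A difference in mortality that individual causality judgements miss can be detected only by comparing the arms, and the IDSMC is the body that sees this comparison while the trial runs. It can work only from what has been sent in. If sites follow the reporting sections to the letter, a death after week 17 that is judged unrelated need not be entered until week 52.

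Two features sharpen the point. First, the wording in section 10 ties entry to a follow-up visit, which a participant who has died will not have. Second, the 24-hour route depends on a causal link to the trial intervention. A death under usual care is unlikely to be judged so linked, so the deferred route probably carries nearly all control-arm deaths, and the interim comparison depends on it.

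The protocol itself treats death as common in this condition. Section 3.1 states: "Mortality is high with 14-58% dying within the following 12 months".

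**Working it through.** **Inputs.** Visits at 17 and 52 weeks after randomisation (section 9.1). Recruitment planned as "recruit participants over 14 months" (section 11.2.1). Sample size 446 (section 11.2). One-year mortality 14%, the low end of the range in section 3.1, used as an assumption and varied below.

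**The plan's own sample size.** 2 × (1.960 + 1.2816)² × 10² × (1 − 0.52) / 2.4² = 175.1, so 176 per arm and 352 in total; 352 / 0.79 = 445.6, so 446. The stated figure is reproduced.

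**Timing.**
- Longest wait for a death just after week 17: 52 − 17 = 35 weeks.
- One month is 365.25 / 12 / 7 = 4.348 weeks, so 14 months is 60.9 weeks.
- Week 17 of the first participant falls at 17 / 4.348 = 3.9 months, and week 52 at 52 / 4.348 = 12.0 months.
- Between these dates no unrelated death after week 17 need be entered. That is 35 / 60.9 = 57% of planned recruitment, about 8 of 14 months.

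**Illustration at month 12** (T = 52.18 weeks). Assume uniform accrual, a constant hazard, every death judged unrelated, and entry at the nominal visit date even though no visit takes place. Accrual a = 446 / 60.875 = 7.327 per week. Hazard h = −ln(0.86) / 52 = 0.00290 per week.
- All deaths so far: a × [T − (1 − e^(−hT))/h] = 7.327 × (52.18 − 48.42) = 27.5.
- Deaths by week 17 in participants who have passed week 17: a × (T − 17) × (1 − e^(−17h)) = 7.327 × 35.18 × 0.0481 = 12.4. These are due for entry. The very few participants past week 52 add 0.1, giving 12.5.
- Deaths after week 17: a × [e^(−17h)(T − 17) − (e^(−17h) − e^(−hT))/h] = 7.327 × (33.49 − 31.84) = 12.1, of which 0.1 are due for entry.
- The remaining 27.5 − 12.4 − 12.1 = 3.0 deaths are in participants not yet at week 17.

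**Other mortality rates and month 14** (same method, follow-up capped at 52 weeks). Each cell gives deaths due for entry / deaths that have occurred.

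| One-year mortality | Month 12, all | Month 12, after week 17 | Month 14, all | Month 14, after week 17 |
|---|---|---|---|---|
| 5% (assumed) | 4.3 / 9.7 | 0.0 / 4.3 | 7.5 / 12.9 | 2.2 / 6.5 |
| 10% (assumed) | 8.8 / 19.5 | 0.1 / 8.7 | 15.2 / 25.9 | 4.3 / 12.9 |
| 14% | 12.5 / 27.5 | 0.1 / 12.1 | 21.4 / 36.4 | 6.0 / 18.0 |
| 58% | 64.1 / 127.0 | 0.4 / 47.3 | 101.0 / 164.0 | 21.7 / 68.5 |

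The counts move with the mortality rate, but the shares hardly do. At month 12 about 45% to 50% of all deaths, and about 1% of those after week 17, need be in the database. At month 14 the shares are about 58% to 62% and about one third.

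**The case against.** The strongest reply is that the rule sets a latest date and does not forbid earlier entry. Sections 9.2.1 and 10 have events recorded on awareness, and therapy teams are told how to enter them. Serious events go to the IDSMC periodically, and the committee sets its own meeting frequency. The IDSMC charter and the monitoring plan are cited but not shown, and either may contain a death notification. The intervention is described as low risk and is delivered within 16 weeks of surgery, so deaths during treatment are due at week 17. All of this stands. It shows that deaths may arrive earlier, but the protocol does not require it. Early entry left to choice may also be uneven, because the therapy teams given entry instructions are those delivering the intervention.

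Some stronger readings are tempting, but the documents do not support them:

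- That the IDSMC is blind to mortality, or blind for nearly all of recruitment. Deaths by week 17 are due much sooner, and the window for later deaths runs from about month 4 to month 12.
- That a death has no entry point at all. Section 10.8.2 gives a time, which does not require an attended visit. Only section 10 uses the visit wording. Reasons for non-completion are recorded (section 3.4.3) and missing data are queried (section 13.2.1).
- That 446 × 0.14 = 62 deaths are to be expected. The cited range is for hip fracture patients in general. This trial excludes care-home residents and people lacking capacity (section 6.2), and the phase II cohort was more likely to die than the feasibility-trial participants (section 3.2.3.2).
- That complete withdrawal is a gap in the rule. Section 9.3.5 ends data collection at that point by design.
- That the primary analysis is harmed. Entry by week 52 precedes database lock, and the handling of deaths is commonly left to the statistical analysis plan, which is not at hand.

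**Conclusion.** The point holds as a gap in interim reporting. Following the protocol exactly, a site may leave a death judged unrelated out of the database for up to 35 weeks. For about 8 of the 14 planned recruitment months, deaths after week 17 need not be available to the committee charged with interim safety monitoring. After that, entry catches up only gradually. The 35-week wait and the window follow from the visit schedule and the planned recruitment period alone, and the window would be a smaller share if recruitment overran. The death counts are illustrative and rest on the accrual, hazard and mortality assumptions stated. This is a cheap improvement to a stated rule. It does not show that the trial's safety endpoint or its primary result is wrong.

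**What to change.** - Keep deferred entry for non-fatal SAEs judged unrelated.
- Amend sections 10, 10.8.2 and 10.9 so that every death, with date and cause and whatever the causality judgement, is entered in the trial database when the site becomes aware of it, in both arms and whether or not a visit takes place.
- State that deaths by arm are reported to the IDSMC at each meeting.
- Reconcile sections 9.2.1, 10, 10.8.2 and 10.9, so that recording on awareness and the date of database entry are no longer left at odds.

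The cost is a little site time brought forward: the same information is entered earlier, for the participants who die. No assessment, analysis or aspect of clinical care changes.

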10.9 Responsibilities – Site Principal Investigator

The site Principal Investigator is responsible for recording and reporting to CTRC all safety events that are observed or reported during the trial, regardless of their relationship to the trial. All serious events related to intervention (SAEs / related SAEs / RUSAEs) must be reported immediately by the investigator to the CTU on an SAE form. All other adverse events and serious adverse events not related to intervention should be reported on the regular progress/follow-up reports.

Minimum information required for reporting

- Trial randomisation number
- Sponsor trial number
- One identifiable coded subject
- One identifiable reporter
- A causality assessment
- I. The SAE form should be completed by a designated investigator, a physician named on the 'signature list and delegation of responsibilities log' as responsible for reporting serious safety events and making trial related medical decisions. The investigator should assess the event for the likelihood that it is a response to the trial intervention. In the absence of the designated investigator the form should be completed and signed by an alternative member of the research site trial team (as named on the delegation log) and submitted to the CTRC. As soon as possible thereafter the responsible investigator should check the SAE form, make amendments as appropriate, sign and re-send to the CTRC. The initial report shall be followed by detailed reports every 5 days until resolution.
- II. When submitting a SAE to the CTRC research sites should also telephone the appropriate trial co-ordinator on telephone number [name] to advise that an SAE form has been submitted.
- III. Send the SAE form by fax (within 24 hours or next working day) to the CTU:

[contact]

- I. The responsible investigator must **notify** their R&D department of the event (as per standard local governance procedures).
- II. The participant must be followed-up until clinical recovery is complete and laboratory results have returned to normal, or until the event has stabilised. Follow-up may continue after completion of protocol treatment if necessary.
- **III.** Follow-up information is noted on another SAE form by ticking the box marked 'follow-up' and returning to the CTRC as information becomes available. Extra, annotated information and/or copies of test results may be provided separately.
- IV. The patient **must** be identified by trial number, date of birth and initials only. The patient's name **should not** be used on any correspondence.

